Marijuana abuse is growing in the age group we are studying (20-60 years) and may continue to increase as other states in addition to Washington and Colorado legalize marijuana. There is a high rate of co-use with nicotine and given we are successfully recruiting nicotine dependent subjects we feel that we have an exceptional opportunity to capture this comorbid population and examine effects of progesterone treatment for cessation of marijuana.

Specific Aims

This study will be similar to the ongoing double-blind clinical trial of Progesterone (PRO) vs. placebo (PBO) for cigarette smoking cessation which is successfully being conducted (currently in year 4 of 5). We will enroll a parallel participant group of marijuana smokers who are co-using nicotine cigarettes, randomized 1:1 to PRO vs. PBO in a pilot double-blind trial, adjusting the protocol to address our time constraints. Our aims are:

Primary Aim: To estimate the association between PRO vs. PBO and percent reduction of marijuana use in

males and females who are co-users of cigarettes.

Hypothesis 1a. Males and females randomized to exogenous PRO will have greater percent reduction in marijuana use compared to those randomized to placebo.

Hypothesis 1b. Males compared to females, regardless of randomization, will have greater percent reduction of marijuana use.

Hypothesis 1c. Males and females, regardless of randomization, with higher levels of serum progesterone, will have a greater percent reduction in marijuana use.

Exploratory Aim: To estimate the association between impulsivity and percent reduction in marijuana use in males and females who are co-users of cigarettes.

Hypothesis 2a. Males and females with lower impulsivity at baseline will have greater reductions in marijuana use.

Hypothesis 2b. Higher serum levels of progesterone in males and females are predicted to reduce impulsivity and marijuana use.

Methods

Study Design, Recruitment and Subject Sample

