Baseline Visit (Visit 3): Female subjects will be instructed to come into the clinic within three days of the start of their Luteal Phase for their baseline visit and to start medication (PRO or PBO). Female subjects will self-report menstrual cycle length at their screening visit and staff will determine when their Luteal Phase will most likely begin. Male subjects will be instructed to come into the clinic according to their assigned delay (per randomization list generated by the Statistical Analysis Core). This visit will occur seven days prior to quit date. At this visit, subjects will be randomized to PRO or PBO within strata defined by sex. The Statistical Analysis Core (SAC) will generate the randomization tables (one for each sex, 1:1 allocation using randomly permuted blocks of size 2 and 4), and the Clinical Trials Research Pharmacy will use it to determine randomization assignment. Randomization assignment will be stored in a secure file in a secure location at the Clinical Trials Research Pharmacy, to be shared only with the SAC. All other project staff including PI and study coordinator, as well as the participant, will remain blinded to the randomization assignment. At the baseline visit subjects will provide a blood sample (for hormone assessment), urine sample for THC, breath sample (to confirm smoking status via carbon monoxide breathalyzer), have their vital signs (blood pressure, heart rate, weight) measured, be informed of their quit date, and receive brief behavioral counseling to prepare for their quit date. At the end of this visit subjects will be compensated for their time, given study medication along with instructions for taking the medication (beginning at 8PM that day), as well as a clinic visit schedule for the remaining clinic visits. This visit will take approximately one hour to complete.

Marijuana Change Date Assignment: Change date (Week 0) will be set for 7 days following the Baseline Visit. Since this entails a delay of variable duration from Screening Visit 2 to Baseline Visit (thus impacting timing of medication initiation) across female subjects, each male subject will be matched to a female subject for a similar delay so that, across the male and female groups, study procedures will follow a similar chronology.

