- Weeks 0-5 (Visits 4-9):** The Week 0 clinic visit will occur on the assigned “Marijuana Change Date”. Subjects will attend clinic visits on a weekly basis thereafter for 5 weeks. At weeks 0, 2, 4, and 5, blood samples will be collected and stored for the analysis of hormones. Urine samples will be collected at each

clinic visit for the visual inspection of riboflavin (assessing medication compliance), biochemical confirmation of THC, and for a pregnancy test (females only). Urine will be saved and stored on Weeks 0, 2, 4, and 5 for cotinine analysis.

Subjects will also complete several forms and questionnaires (described below). Subjects will return the medication bottle and unused medication, be given a new one-week supply and adverse events will be assessed. At Week 4, subjects will complete impulsivity tasks and study medication will be discontinued. Finally, subjects will receive brief, behavioral counseling at each clinic visit. At the end of each visit subjects will be paid for their time. These visits will take approximately 30-45 minutes to complete.

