Progesterone: The progesterone will be given in the form of an active or placebo micronized natural progesterone (generic Prometrium). All subjects will take 200 mg twice daily (approximately 8am and 8pm) for five weeks starting seven days prior to the assigned change date. The dosage was selected to ensure that serum progesterone levels will be consistent with those observed in the natural Luteal phase of the menstrual cycle (6-14 ng/mL) since that phase has been shown to be favorable for smoking cessation ([name] et al 2008). We expect the following serum progesterone levels by group (Figure 5): (1) females + PRO 9-13 ng/mL; (2) males + PRO 6-7 ng/mL; (3) females + PBO, varies by menstrual phase from 1-14 ng/mL; and (4) males + PBO 0-1 ng/mL (Goletiani et al 2007; Reed et al 2010; Yen et al 1999). Delivery of exogenous progesterone has been successfully used in other studies and is generally well tolerated (Sofouglu et al 2001; Sofouglu, et al 2004; Goletiani et al 2007; Reed et al 2010). The most common adverse effect in males and females is sedation. Less common effects include breakthrough bleeding (females), nausea (females and males) and breast tenderness (females) (de Lignieres, 1999; Goletiani et al 2007). While it is possible that progestins may contribute to risk for thromboembolism, we will be using natural micronized progesterone instead of synthetic progestins. Natural micronized progesterone is not known to be associated with thromboembolic risk (PDR, 2002; Goletiani et al 2007), and consequently is a safer choice. Micronized progesterone is not a form of birth control. Therefore, all female subjects will be educated on the importance of using a double-barrier method to protect against pregnancy.

Study Measures

We will assess marijuana use using two methods (self-report, biochemical confirmation). *First*, at each clinic visit the TimeLine Follow-Back (TLFB) method will be completed. The TLFB is a validated retrospective data capture technique (Sobell et al 1996). *Second*, at each clinic visit we will measure urinary THC levels (see table 1 for all study measures and when they are collected).

Impulsivity Measures: Subjects will complete *three self-report measures* that have been computerized at each clinic visit beginning at Screening Visit 2. These measures will assess the characteristics of impulsivity, inhibition, planfulness, and cognitive impairments, key areas of focus in this grant.

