Addressing Hypothesis 1a: An unadjusted assessment of the treatment effect will come from a linear model of percent reduction in marijuana use on randomized treatment assignment, separately by sex. **Hypothesis 1b:** A linear model including both males and females will be used to estimate the overall gender effect on percent reduction in marijuana use. **Hypothesis 1c:** A linear model including both males and females will be used to estimate the association of serum progesterone with percent reduction in marijuana use; we will separately consider baseline progesterone, cumulative progesterone (summed over weeks 0-4), and week 4 progesterone.

Addressing Hypothesis 2a: A linear model including both males and females will be used to estimate the association of impulsivity with percent reduction in marijuana use. **Hypothesis 2b:** A linear model including both males and females will be used to estimate the interaction between baseline impulsivity and baseline serum progesterone on percent reduction in marijuana use.

Missing data plan: Quality assurance plans are described below. The primary outcome analysis will be carried out using two parallel models: one model will exclude subjects for whom we were unable to obtain a week 4 TLFB or urine THC. Since 'missing at random' is a strong statistical assumption to make, we will also carry out a parallel model that uses multiple imputation of the week 4 TLFB and urine THC based on an individual's previous visits' TLFB and urine THC levels. We will also examine whether persons missing their week 4 visit differed in their baseline characteristics or treatment assignment from persons not missing their week 4 visit.

Power: This is a pilot study to generate data to potentially motivate and justify a future fully-powered study of PRO and marijuana use. This study will estimate magnitude and direction of treatment effects and associations with impulsivity (sex-specific and overall). Hence, no power calculations are provided.

Data Safety and Monitoring Plan, Board, and Administration.

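### Hypothesis 1c: week 4 and cumulative progesterone depend on capsule taking in the progesterone arm, so better adherers who also cut down more would create a modest false association that the planned arm adjustment leaves in place

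*Combined protocol and SAP*

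**What the plan says.** Specific Aims places this hypothesis under the Primary Aim: "Males and females, regardless of randomization, with higher levels of serum progesterone, will have a greater percent reduction in marijuana use". The Analysis Plan tests it with one model pooling sexes and arms: "A linear model including both males and females will be used to estimate the association of serum progesterone with percent reduction in marijuana use". On the exposure it adds: "we will separately consider baseline progesterone, cumulative progesterone (summed over weeks 0-4), and week 4 progesterone".

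- **Timing of exposure.** At the Baseline Visit blood is taken and medication is then handed out, with the first dose that evening. Later draws are set in Weeks 0-5: "At weeks 0, 2, 4, and 5, blood samples will be collected and stored for the analysis of hormones". Medication stops at the Week 4 visit, so the weeks 0-4 sum rests on three single draws.
- **Dosing.** Study Medication says: "All subjects will take 200 mg twice daily (approximately 8am and 8pm) for five weeks". No draw time or dose-to-draw interval is specified.
- **Expected levels** (Study Medication): men 6-7 ng/mL on progesterone and 0-1 on placebo; women 9-13 on progesterone and 1-14 on placebo, by menstrual phase.
- **Adherence data** (Weeks 0-5). Urine at each visit is used for "visual inspection of riboflavin (assessing medication compliance"), and "Subjects will return the medication bottle and unused medication". No model in the Analysis Plan uses either.
- **Adjustment.** The Analysis Plan calls for unadjusted and adjusted estimates. The adjusted ones include treatment assignment and an open list of covariates (age, baseline progesterone, estradiol and baseline impulsivity are the examples). Adherence is not named. People who never took their capsules stay in the analysis.

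**The concern.** Keeping non-takers is right for the randomised comparison in Hypothesis 1a. Hypothesis 1c instead regresses outcome on a level measured after randomisation. A treated person who skips capsules enters with a low value; one who takes them enters with a high value. Reliable capsule takers may also be the people who follow the counselling to change their use, in either arm. The model would then credit progesterone with an effect of reliability.

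The pilot exists to estimate magnitude and direction for a fully powered trial. This bias acts on exactly those quantities, in the hypothesised direction, and could pass for exposure-response support when the drug does nothing.

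**Working it through.** The plan states no alpha, power, effect size or SD, so there is no figure of its own to reproduce.

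**Inputs from the documents.** Midpoints of the expected levels: men 6.5 (progesterone) and 0.5 (placebo); women 11 and 7.5. Each range is treated as uniform, variance = width²/12. Study Design gives 20 per arm, half female, so 10 per sex-by-arm cell.

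**Assumptions.** No drug effect; a fraction q non-adherent in both arms; a non-adherent treated person has the placebo level for their sex; adherent people reduce d points more in both arms; outcome SD 35.

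**Step 1: capsule share in treated men.** From (6 − 1)/6 = 83% to (7 − 0)/7 = 100%. For women no such share can be isolated, because 1-14 overlaps 9-13.

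**Step 2: covariance of progesterone with outcome.** It equals q(1 − q) × d × the level gap due to adherence, averaged over the four cells: (6 + 3.5 + 0 + 0)/4 = 2.375.
- q = 0.25, d = 20: 0.1875 × 20 × 2.375 = 8.91
- q = 0.40, d = 30: 0.24 × 30 × 2.375 = 17.1

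**Step 3: unadjusted slope (covariance / total variance).**
- q = 0.25: the weights are 0.3125 at 0.5, 0.1875 at 6.5, 0.3125 at 7.5 and 0.1875 at 11. The mean is 5.78 and the mean square, including within-range variance, is 52.96. Variance 52.96 − 33.42 = 19.54; slope 8.91/19.54 = 0.46.
- q = 0.40 (weights 0.35 and 0.15): variance 49.43 − 29.43 = 20.00; slope 17.1/20.00 = 0.85.

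**Step 4: slope with arm and sex terms.** The covariance is unchanged, but only within-cell variance (plus the small arm-by-sex remainder) is left to divide by.
- q = 0.25: placebo men 0.08; placebo women 14.08; treated men 0.08 + 0.1875 × 36 = 6.83; treated women 0.75 × 1.33 + 0.25 × 14.08 + 0.1875 × 12.25 = 6.82. Mean 6.95, plus ((4.5 − 2.625)/4)² = 0.22, gives 7.17. Slope 8.91/7.17 = 1.24.
- q = 0.40: treated men 8.72, treated women 9.37; mean 8.07, plus ((3.6 − 2.1)/4)² = 0.14, gives 8.21. Slope 17.1/8.21 = 2.08.

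Arm adjustment discards the randomised variation in progesterone and keeps the adherence-driven part, so the false slope rises.

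**Step 5: simulation of the same set-up**, 40 people, q 0.25-0.40, d 20-30. The 2.5% benchmark is one tail of an assumed two-sided 0.05.

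| Model | False slope (points per ng/mL) | False positive-direction results |
|---|---|---|
| Pooled, unadjusted | 0.4-0.8 | 5-9% |
| With arm and sex | 1.2-2.1 | 8-15% |
| With arm, sex and accurately measured adherence | about 0 | 2.4-3.5% |

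If 20% of adherence values are misclassified, only about a quarter to a third of the bias goes. The standard error of the slope is about 1.3, 2.2 and 2.4 in the three models.

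**Step 6: a second set of assumptions.** Graded adherence (Beta(2,1)), adherence-outcome correlation 0.3, dose-to-draw noise of log-SD 0 or 0.5, two-sided 0.05: false positives were 5.8-6.5% unadjusted, 6.7-9.1% with arm and sex, and 8.1-20.4% within the progesterone arm alone. With correlation 0 all were about 5%, with or without timing noise. Noise shrank the false slope.

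These slopes are in week 4 units. The three-draw sum is on a different scale, but the mechanism is the same.

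**The case against.** The other side has real points.

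- **It is a pilot.** Hypothesis 1c is worded as an association, with no alpha and no power claim, and Hypothesis 1a is untouched. That stands, and it limits the consequence. It does not remove the bias in the quantity the pilot sets out to estimate.
- **Arm adjustment is already planned and the covariate list is open.** True, but arm adjustment does not cure confounding within the arm, and the named examples do not include adherence.
- **The premise is unproven.** The documents neither quantify adherence nor show that adherers cut down more. If they do not, there is no false association.
- **The available adherence measures are crude.** Riboflavin is judged by eye, and returned medication is collected without a stated count. Adjustment will be partial.

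A reader might also infer more than the documents support:

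- **That serum progesterone mainly shows who took the capsules.** This is supported for treated men only; untreated women alone span 1-14 ng/mL. Even in men a low value does not prove missed capsules: draw timing varies, and the Trial Safety section allows a dose reduction on active drug.
- **That the artefact is about 8 points, with 10-24% false positives.** Those figures come from giving all 20 people per arm the men's levels: (0.1875 × 20 × 3)/(0.625 × 0.375 × 36) = 11.25/8.44 = 1.33 per ng/mL, or 8 points over 6 ng/mL. The plan has 10 men per arm and a model that pools women.
- **That unrecorded dose timing creates a false association.** Unless linked to behaviour, it adds noise and weakens the slope.

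**Conclusion.** The concern holds for two of the three Hypothesis 1c exposures, week 4 and cumulative progesterone. They are post-randomisation measures that depend on capsule taking in the progesterone arm, and no planned model deals with that. The baseline progesterone model and the randomised comparison in Hypothesis 1a are not affected.

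The size is modest in the planned unadjusted model: false positive-direction results at roughly two to four times the nominal 2.5%. It is larger in the arm-adjusted form, 8-15% once sex is also included. All of this rests on assumed non-adherence, an assumed adherence gap in outcome and an assumed SD. The documents supply only the expected levels and the cell sizes. It is worth correcting before analysis because the needed specimens and returns are already collected.

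**What to change.** For week 4 and cumulative progesterone only:

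1. Add a sex term and adherence (riboflavin result at each visit and a count of returned capsules) to the planned arm-adjusted model. Report it beside the planned models.
2. In the placebo arm, check whether adherence predicts percent reduction. An association there cannot be due to progesterone capsules, so it serves as a negative control. This assumes that the adherence marker is present in both capsules.
3. Label the on-treatment Hypothesis 1c estimates non-causal, and name Hypothesis 1a as the evidence on drug effect.
4. Record the time of the last dose and of the draw at each on-treatment blood sample, to reduce noise in the exposure.

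Do not offer slopes within the progesterone arm alone as a remedy, since they show the artefact most strongly. In treated men with d = 20 the slope would be about 20/6 = 3.3 points per ng/mL with no drug effect.

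The cost is one more model, a capsule count and two time fields, with no new visits or samples. Precision falls slightly against the arm-and-sex model (standard error about 2.4 against 2.2) and clearly against the unadjusted pooled model (about 1.3). If adherence is measured crudely, part of the bias remains.

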Illicit drug users appear to be more impulsive than non-users (Bickel et al 2001) and sex differences have been observed in this association such that females are more susceptible to the effects of impulsivity than men (Nieve et al 2011). Preliminary evidence suggests sex hormones may play a role as females who have recently quit smoking have less impulsive behavior while in the luteal phase than in the follicular phase ([name] et al 2009a). Further, within the animal literature, delivery of exogenous progesterone has been shown to decrease impulsive behavior (Llaneza & Frye, 2009).

Taken together, these data suggest that progesterone may improve marijuana use outcomes perhaps by reducing impulsive behavior. However, the clinical literature on this topic is lacking. Therefore, in this pilot study, we are proposing a double-blind randomized controlled trial to assess the role of exogenous progesterone on impulsivity and change in marijuana use in a sample of males and females who are co-users of marijuana and nicotine cigarettes. In the first 3 years of our P50 SCOR entitled "Sex Differences and Progesterone: Effects on Impulsivity, Smoking and Cocaine Abuse" (P50 DA033942, [name] PI) we have noted an immediate opportunity to follow an interesting and potentially important finding. In Project 1 entitled "Sex Differences and Progesterone: Effects on Impulsivity and Smoking Cessation" we have found that a large percentage of subjects screened have marijuana use concurrent with their nicotine dependence (23% of 1704 screening phone calls), and were therefore ineligible for the nicotine study. With IRB approval, we have already been collecting additional screening data on these concurrent nicotine and marijuana users to prepare for a future application on the efficacy of progesterone as treatment for marijuana addiction.

As the number of marijuana users has continued to grow in Minnesota, with approximately 8% of the population reporting to have used marijuana within the last year, we have an excellent opportunity in our demographic area, and it would be informative to carry out a pilot study on the effects of progesterone (vs placebo) on this population that are co-users of marijuana and nicotine and to compare them to the nicotine group currently being studied.

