- *Behavioral Inhibition/Activation scales (BIS/BAS)*: 20-item form is commonly used to study externalizing tendencies (Carver and White, 1994). Investigators in Project II have used this instrument with success.
- *Barratt Impulsiveness Scale (BIS)*: 30-item self-report measure of self-control (Patton et al 1995). Doran and colleagues (2004) demonstrated that impulsivity, as measured with this item, was a predictor of smoking relapse.
- *Brief Self Control Scale (BSCS)*: This item consists of 13 questions rated on a 4-point scale from “very true” to “very false” on items reflecting the ability to control problematic behaviors (Tangney et al 2004).

The *Impulsivity Tasks* represent two forms of impulsivity, 1) impaired cognitive inhibitory mechanisms, and 2)

deficits in motor inhibitory mechanisms. “Delay discounting” entails higher-level cognitive inhibitory processes that may characterize the behavior of individuals who are drug dependent (Bickel and Marsch, 2001) tobacco users (Baker et al. 2003), cocaine users (Monterosso et al, 2001), other drug users (e.g. Vuchinich and Simpson, 1998; Kollins, 2003) and pathological gamblers (Dixon et al, 2003). The following items will be completed at Screening Visit 2 and Week 4.

- **Delay Discounting Task:** Developed by de Wit and colleagues (Richards et al, 1999), delay discounting refers to the reduction in value of a reward over time relative to its immediate worth. One’s discount rate, also known as a time preference, is a measurable individual difference and involves a series of choices (e.g. Petry and Casarella, 1999): one option is an immediate payment (e.g. \$1); the second option is a larger payment (e.g. \$50) after a delay (e.g. 6 hours to 25 years). Titrating the payment amounts at each delay interval allows the identification of points of indifference (the point at which the subject switches from choosing the immediate to the larger reward at a given delay interval). We additionally included a probability discounting condition to measure risk aversion in addition to time preference (Richards et al, 1999).

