- **GoStop Task:** This task measures response inhibition. A series of five-digit numbers are presented on a computer monitor at a rate of 500ms for ever two seconds. Subjects are instructed to click the mouse button when the number they see is identical to the previous number. Half of the numbers change color from black to red at 50, 150, 250 and 350. Subjects are instructed to respond to the matching number only when the displayed number is black. The primary outcome of this task is the percent of inhibition failures for the 150ms delay (Dougherty et al 2008). This item has been successfully used to assess tobacco dependence and smoking behavior (Billieux et al 2010).
- **Balloon Analogue Risk Task (BART):** This task, with 30 replications/session, is a measure of risk-taking. It involves displaying a small balloon on a computer screen. Each “pump” to inflate the balloon accumulates five cents, with each pump potentially breaking the balloon. The average pumps to the breaking point is 64. To ensure attentive responding, subjects will receive the actual amount of money accrued on this task. The primary outcome on this task was the number of exploded balloons divided by the number of trials (Lejuez et al, 2002).
- **Immediate Memory Task / Delayed Memory Task (IMT/DMT):** This task is a continuous performance task that has two phases. First, the IMT displays a series of five-digit numbers in on a computer monitor for 500 ms followed by a blank screen 500 ms. Subjects click the mouse button whenever an identical number is displayed. Next, the DMT requires the subject to remember a five-digit number and compare it to another that is presented 3.5 seconds later. During the 3.5 interval subjects are presented with a distracter (12345) and told to ignore it. The primary outcome of this task is the IMT/DMT ratio which is defined as the proportion of commission errors to correct detections (Mathias et al 2002). This item is included as it we have used it in prior studies to identify menstrual phase differences in impulsivity and attention (see Preliminary Studies B.2.1.), and therefore is expected to be sensitive to the group differences in sex and progesterone.

Independent Measures (sex, randomization, and serum progesterone):

Sex will be collected via self-report on the Demographics form completed at Screening Visit 1.

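### The only model planned for Hypothesis 2b cannot show whether progesterone lowers impulsivity: impulsivity is never an outcome, and both predictors are measured before the first dose

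*Combined protocol and SAP*

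**What the plan says.** The background text before Specific Aims says the trial is "to assess the role of exogenous progesterone on impulsivity and change in marijuana use". Under Specific Aims, the Exploratory Aim is "To estimate the association between impulsivity and percent reduction in marijuana use in males and females who are co-users of cigarettes", and beneath it Hypothesis 2b reads: "Higher serum levels of progesterone in males and females are predicted to reduce impulsivity and marijuana use".

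The Analysis Plan gives Hypothesis 2b one linear model, in males and females together, to "estimate the interaction between baseline impulsivity and baseline serum progesterone on percent reduction in marijuana use". The Hypothesis 2a model relates impulsivity to the same marijuana outcome. The plan's general paragraph also names baseline impulsivity among the possible adjusting covariates.

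On data collection, the Impulsivity Tasks section says of its four tasks: "The following items will be completed at Screening Visit 2 and Week 4". The Weeks 0-5 section adds: "At Week 4, subjects will complete impulsivity tasks and study medication will be discontinued". Three self-report impulsivity scales are completed at every visit from Screening Visit 2. Blood for progesterone is drawn at screening, at baseline and at Weeks 0, 2, 4 and 5. The memory task (IMT/DMT) is justified by earlier findings "and therefore is expected to be sensitive to the group differences in sex and progesterone".

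**The concern.** In Hypothesis 2b progesterone is the cause and impulsivity is one of two outcomes. In the model, impulsivity is a predictor and marijuana use is the only outcome. An interaction between two pre-drug measurements asks whether the link between a person's own progesterone and later marijuana reduction varies with how impulsive that person was at entry. That is a fair question, but it is not whether progesterone reduces impulsivity.

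The pilot exists to supply estimates that might justify a larger trial, and reduced impulsivity is the route it proposes for any benefit. As written, the plan would finish without a pre-specified estimate of that step. If it stays so, whoever examines the step later would choose among seven instruments, four of which have no named summary score.

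**Working it through.** The plan gives no figure to reproduce, because it states no power, effect size or SD. The mismatch rests on the text.

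**Step 1: hypothesis against model.**

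| | Predictor | Outcome |
|---|---|---|
| Hypothesis 2b as stated | Serum progesterone | Impulsivity; marijuana use |
| Hypothesis 2b as modelled | Baseline impulsivity × baseline progesterone | Marijuana use |
| Hypothesis 2a as modelled | Impulsivity | Marijuana use |
| Hypothesis 1c as modelled | Progesterone (baseline, cumulative, Week 4) | Marijuana use |
| Hypotheses 1a and 1b as modelled | Arm; sex | Marijuana use |

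Impulsivity never appears in the outcome column. Hypothesis 1c supplies the marijuana half of Hypothesis 2b; nothing supplies the other half.

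**Step 2: timing.** Baseline blood is drawn at the Baseline Visit. Medication is handed out at the end of that visit, with the first dose at 8 PM that day. The tasks are done before drug only at Screening Visit 2. The self-report scales are done at Screening Visit 2 and at the Baseline Visit, both before the first dose. Whichever pre-drug score is used, neither term of the interaction can reflect exposure to study drug.

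**Step 3: are the needed data collected?** Yes. Four tasks plus three scales make seven measures, each taken at Screening Visit 2 and at Week 4, the visit at which drug stops. On-treatment progesterone is available at Weeks 0, 2 and 4.

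**Step 4: precision of the missing arm model.** Take Week 4 impulsivity on arm, sex and the Screening Visit 2 score, with 40 complete subjects (20 per arm). Residual degrees of freedom are 40 − 4 = 36 and t = 2.028. In units of the within-arm SD:

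- half-width = t × √(2/n per arm) × √(1 − r²), where r is the correlation between the Screening Visit 2 and Week 4 scores;
- r = 0: 2.028 × √(2/20) = 0.64;
- r = 0.5 (assumed): 0.641 × 0.866 = 0.56;
- r = 0.7 (assumed): 0.641 × 0.714 = 0.46.

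Fitted within one sex (10 per arm, 17 degrees of freedom, t = 2.110), the half-width is 2.110 × √(2/10) = 0.94, or 0.82 and 0.67 at the same two correlations.

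**Step 5: number of estimates.** Two models on seven measures give 14 estimates. If no effect exists, 14 × 0.05 = 0.70 of the 95% intervals are expected to exclude zero. If the estimates were independent, the chance of at least one would be 1 − 0.95^14 = 0.51. They will be correlated, so 0.51 is only a guide.

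**Step 6: missing Week 4 scores.** The design enrols 70 to obtain 40 Week 4 outcomes. The missing data plan imputes only the Week 4 marijuana timeline and urine THC, and the telephone or e-mail follow-up recovers only recalled marijuana use. Without a further rule, Week 4 impulsivity would be analysed in attendees alone.

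**The case against.** The strongest reply is that this is an exploratory hypothesis in a pilot without power calculations, and that the interaction fits the Exploratory Aim, which treats impulsivity as a predictor. Hypothesis 1c already covers progesterone and marijuana use. The Analysis Plan also states an intent to estimate treatment effects and associations with impulsivity. Much of this stands. The interaction is legitimate, the exploratory status limits the weight of the point, and the marijuana half is covered. What does not follow is that the impulsivity half is covered: a general statement of intent is not a model, and the hypothesis-by-hypothesis list contains none.

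Three stronger readings are tempting, but the documents do not support them.

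- A reader might infer that the mechanism can now be studied only post hoc. Analyses are scheduled for the end of the study, and all staff except the statistical core and the pharmacy are blinded, so a plan amended before unblinding would still be pre-specified.
- A reader might infer that the efficacy comparison is compromised. Hypothesis 1a is a randomized comparison fitted separately by sex and uses none of these terms.
- A reader might extend the criticism to Hypothesis 1c because its pooled model names no sex term. That model estimates the association as the hypothesis words it. The plan also promises adjusted as well as unadjusted assessments, with an open covariate list, so whether sex is included cannot be judged from these documents.

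**Conclusion.** The point holds as a mismatch between a stated hypothesis and its model, and it should be fixed. Progesterone's effect on impulsivity, which Hypothesis 2b predicts and the background names as a purpose, has no planned estimate although every measurement needed is scheduled. The conclusion depends on no assumed effect size. Only the precision figures carry assumptions: 20 complete subjects per arm, no gain from the sex term, and a baseline correlation between 0 and 0.7. On those terms the arm effect would be known to within about 0.46 to 0.64 SD. That is enough to indicate direction and rough size for planning, but not to confirm a mechanism.

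**What to change.** Amend the Analysis Plan before unblinding, with the wording settled by staff who do not hold the assignments:

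1. Add a linear model of Week 4 impulsivity on randomized arm, sex and the Screening Visit 2 score. This answers the purpose in the background text.
2. Add a model of Week 4 impulsivity on on-treatment progesterone (Weeks 0, 2 and 4), with sex and the Screening Visit 2 score. This answers Hypothesis 2b as worded. Label it observational, because serum level is only partly set by randomization.
3. Fix one summary score per instrument in advance. The protocol already names one for GoStop, BART and IMT/DMT. Delay discounting, BIS/BAS, the Barratt scale and the Brief Self Control Scale still need one. Report every measure with a 95% interval as exploratory, and state the count of 14 estimates and the expected 0.70 chance exclusions.
4. Handle missing Week 4 impulsivity as for the primary outcome, with complete-case and multiple-imputation models in parallel.
5. Keep the baseline interaction, relabelled as an effect-modification analysis.

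If only effect modification was intended, Hypothesis 2b should be reworded to say so; the stated purpose would still call for item 1.

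No new visits or samples are needed. The costs are extra analysis, wide intervals, and 14 estimates to be read with restraint. For the tasks, imputation can draw on only one earlier score of the same task (Screening Visit 2), so it will add less there than for the weekly scales.
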